#### **Protocol procedures: blood draws and radiology**

The number of blood draws and frequency of hospital visits in this protocol is within the usual limit of clinical practice for children with these serious underlying diseases. The radiation exposure is increased over routine clinical practice, but within the limits for children who have suffered a fracture and no greater than the exposure during a transatlantic flight. Repeat blood draws and X-rays/DXA will only be requested when absolutely necessary i.e. safety, baseline or end-of-study visits.

In summary, the risks to the children and adolescents in this trial will be minimized by compliance with the eligibility criteria and study procedures, particularly adequate hydration at the time of the infusion, adherence to a diet rich in calcium and vitamin D, regular renal monitoring and contraception in girls of child bearing potential. A maximum dose of 5 mg zoledronic acid (regardless of patient weight) and a minimum 30 minute infusion time 6-monthly are designed to reduce the risk of possible adverse effects. This dose regimen has been used in children with primary and secondary osteoporosis and has shown a favorable risk-benefit profile.

## **4 Population**

The trial population will consist of male and female patients aged from 5 to 17 years old, with a confirmed diagnosis of non-malignant conditions requiring treatment with systemic glucocorticoids (including but not limited to rheumatologic conditions, inflammatory bowel disease, Duchenne muscular dystrophy, nephrotic syndrome) and who have been treated with systemic glucocorticoids (i.v. or oral) within the 12 months preceding screening; with evidence of at least one vertebral compression fracture, or one or more [REDACTED] lower extremity long bone fractures, or two or more [REDACTED] upper extremity long bone fractures, confirmed by central reading. Approximately 92 patients will be randomized from approximately 30 centers in a multicenter setting, to yield at least 82 patients evaluable for the primary endpoint.

### **4.1 Inclusion criteria**

Patients/ eligible for inclusion in this study must fulfill all of the following criteria:

1. Written informed consent must be obtained before any assessment is performed. An assent needs to be provided in accordance with ICH and local regulations.
2. Children, male or female, between 5 and 17 years of age.
3. A confirmed diagnosis of non-malignant conditions requiring treatment with systemic glucocorticoids (including but not limited to chronic rheumatologic conditions or,

inflammatory bowel disease or Duchenne muscular dystrophy) requiring treatment with systemic glucocorticoids (i.v. or oral) within 12 months prior to screening.

- a. Chronic rheumatologic conditions may include: Juvenile Idiopathic Arthritis (JIA): Systemic onset; JIA: Polyarticular rheumatoid factor positive; JIA: Polyarticular rheumatoid factor negative; JIA: Psoriatic arthritis; JIA: Enthesitis-related arthritis; JIA: Oligoarticular arthritis; JIA: Unclassified; Systemic Lupus Erythematosus (SLE); Juvenile Dermatomyositis; Scleroderma (generalized or localized); Overlap Syndromes (including mixed connective tissue disease); Sjogren's syndrome; Systemic Vasculitis, as defined by the Chapel Hill Consensus Conference on Nomenclature: Giant cell (temporal) arteritis, Takayasu's arteritis, Polyarteritis nodosa, Wegener's granulomatosis, Churg-Strauss syndrome, Microscopic polyangiitis, Essential cryoglobulinemic vasculitis, Cutaneous leukocytoclastic angiitis, Behcet's disease, other vasculitis
  - b. Inflammatory bowel disease may include: Crohn's disease and Ulcerative Colitis
  - c. Duchenne muscular dystrophy
  - d. Nephrotic syndrome who have stable normal renal function for at least 3 months prior to screening
  - e. Other subtypes of secondary osteoporosis in children taking glucocorticoids, except patients with oncologic conditions (such as lymphoma and leukemia) [Appendix 7](#).
4. Lumbar Spine BMD - Z score of -0.5 or worse confirmed by the central imaging vendor.
  5. Evidence of at least 1 vertebral compression fracture of Genant Grade 1 or higher or radiographic signs of vertebral compression fracture seen in X-ray within 1 month of or at screening visit, confirmed by central reading. Radiographic signs of fracture include loss of endplate parallelism, vertebral buckling and endplate interruption.

OR

- One or more, low-trauma\*, lower extremity long-bone fracture which occurred sometime within the 2 years preceding enrollment in the study, confirmed by radiological report

OR

- Two or more, low-trauma\*, upper extremity long-bone fractures which occurred sometime within the 2 years preceding enrollment in the study, confirmed by radiological report

\*Low trauma fracture is defined as falling from standing height or less.

## 4.2 Exclusion criteria

Patients fulfilling any of the following criteria are not eligible for inclusion in this study. No additional exclusions may be applied by the investigator, in order to ensure that the study population will be representative of all eligible patients.

1. History of primary bone disease (osteogenesis imperfecta, idiopathic juvenile osteoporosis, rickets/osteomalacia).
2. Any prior use of bisphosphonates, or high dose sodium fluoride (i.e. dental use is permitted).

3. Any medical condition that might interfere with the evaluation of LS-BMD, such as severe scoliosis or spinal fusion. Patients with less than 3 evaluable vertebrae by DXA evaluation in the region of interest L1-L4, as confirmed by the central imaging laboratory, will not be considered eligible for this study.
4. As per investigator's judgment, patient is anticipated to have bone surgery within subsequent year.
5. Hypocalcemia and hypophosphatemia: any value (age-matched) below the normal range at screening.
6. Serum 25-hydroxy vitamin D concentrations of < 20 ng/mL or < 50 nmol/L at screening.
7. Renal impairment defined as an estimated glomerular filtration rate (GFR) < 60 mL/min/1.73 m^2 at screening based on the Schwartz formula at screening
8. A serum creatinine increase between Visit 1 and Visit 2 greater than 0.5 mg/dL (44.2 µmol/L).
9. Uncontrolled symptoms of cardiac failure or arrhythmia.
10. History of hyperparathyroidism or hyperthyroidism within 1 year prior to screening.
11. History of hypothyroidism unless on a stable treatment regimen for > 6 months, with at least one documented normal TSH and FT4 levels during this 6 month period.
12. History of sarcoidosis.
13. Diagnosis of active uveitis (symptomatic or asymptomatic) at the time of enrollment in the study.
14. History of hypersensitivity to any of the study drugs or its excipients or to drugs of similar chemical classes
15. Female patients of child bearing potential are eligible only if they are: (1) not pregnant/ non-lactating; (2) are sexually abstinent or are surgically sterile or (3) if sexually active, must be practicing a medically acceptable form of birth control for greater than 2 months prior to screening visit. Females of child bearing potential who are sexually active must agree to continue to practice their birth control during the trial and at least 1 year after completing the trial and must consent to a pregnancy test prior to every dose administration and at the End of Study (EOS) Visit.
  - [For sites and/or regions where additional safeguards are required e.g. UK, Italy, Germany, Sweden & etc.: Female patients of child bearing potential are eligible only if they are not pregnant/non-lactating. Females of child bearing potential must be practicing a medically acceptable form of birth control for greater than 2 months prior to screening visit. At least one and preferably two complementary forms of contraception including a barrier method should be used and be continued throughout the trial and for at least 1 year after completing the trial. They must also consent to a pregnancy test prior to every dose administration and at the EOS Visit. An additional supervised urine pregnancy test will be assessed at Week 12 (See [Table 6-1](#) and [Section 6.5.5](#)).]
16. History of malignancy of any organ system (other than localized basal cell carcinoma of the skin or *in-situ* cervical cancer), treated or untreated, within the past 5 years, regardless of whether there is evidence of local recurrence or metastases.

## 5 Treatment

### 5.1 Study treatment

#### 5.1.1 Investigational and control drugs

Zoledronic acid (or placebo) 5.0 mg/100 mL solution, supplied in a ready-to-infuse plastic bottle.

#### 5.1.2 Additional treatment

Adequate intake of vitamin D and calcium is mandatory for the four weeks prior to randomization and throughout the duration of the study, i.e. 12 months, either through adequate dietary intake or via supplementation, or a combination of both diet and supplementation. Described below are the recommended guidelines for vitamin D and calcium intake. It is the responsibility of the investigator to ensure that each patient receives the adequate recommended daily allowance of vitamin D and calcium (through diet and/or supplementation).

**Table 5-1 Recommended minimum daily dietary allowances (Ross 2011)**

Age	Vitamin D	Calcium
≥ 5 years to ≤ 8 years	600 IU	1000 mg
≥ 9 years to ≤ 17 years	600 IU	1300 mg

All patients should take at least 600 IU vitamin D daily from Visit 1 until the final Visit through diet and/or supplementation.

Elemental calcium, at least 1000 mg for 5-8 years of age or at least 1300 mg for 9-17 years of age, daily will be taken beginning at Visit 1 and during the total duration of the trial, through diet and/or supplementation. Calcium carbonate is the preferred form of calcium supplementation. If calcium carbonate is not well tolerated, another form of oral calcium would be acceptable.

Any vitamin D and calcium supplements will be recorded on the Concomitant medications/Significant non-drug therapies (e)CRF.

In addition, transient hypocalcemia has been reported especially following the first infusion and it can cause symptoms in rare cases. To prevent the development of symptomatic hypocalcemia, the parent or guardian of each child will receive an information sheet and all patients will receive calcium supplementation at the doses recommended in [Table 5-1](#) starting from the day of infusion and for a minimum of 5 days after each infusion (for sites where this calcium supplementation usually starts prior to the infusion, the total treatment period is approximately 10 days in total) ([Hogler et al 2004](#)).

### 5.2 Treatment arms

At Visit 1, all patients will be counselled regarding adequate dietary intake of calcium and vitamin D with or without supplementation. At Visit 2, each patient will be randomized in a

1:1 ratio within one of two treatment arms to receive either twice yearly 0.05 mg/ kg (max 5mg) i.v. infusion (at least 30 minutes) of zoledronic acid at randomization and Month 6 or twice yearly i.v. placebo at randomization and Month 6.

### **5.3 Treatment assignment and randomization**

At Visit 2, all eligible patients will be randomized via IRT to one of the treatment arms. The investigator or his/her delegate will contact the IRT after confirming that the patient fulfills all the inclusion/exclusion criteria. The IRT will assign a randomization number to the patient, which will be used to link the patient to a treatment arm and will specify a unique medication number for the first package of investigational treatment to be dispensed to the patient. The randomization number will not be communicated to the caller.

The randomization numbers will be generated using the following procedure to ensure that treatment assignment is unbiased and concealed from patients and investigator staff. A patient randomization list will be produced by the IRT provider using a validated system that automates the random assignment of patient numbers to randomization numbers. These randomization numbers are linked to the different treatment arms, which in turn are linked to medication numbers. A separate medication list will be produced by or under the responsibility of Novartis Drug Supply Management using a validated system that automates the random assignment of medication numbers to packs containing the study drug.

The stratification of randomization will occur based on the baseline BMD value category: -2.0 or less vs. -2.0 to -1.0 vs. -1.0 to -0.5 at screening.

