### 9.4.2 Statistical model, hypothesis, and method of analysis

The primary efficacy objective is to demonstrate superiority with respect to the change in LS-BMD Z-score at Month 12 relative to baseline in patients treated with zoledronic acid compared to patients receiving placebo.

Let  $\mu_Z$  and  $\mu_P$  be the population mean of the change in LS-BMD Z-score at Month 12 relative to baseline for patients treated with ZOL and patients receiving placebo, respectively. The null hypothesis of no difference between treatment groups ( $H_0 : \mu_Z = \mu_P$ ) will be tested against the alternative hypothesis that there is difference between treatment groups ( $H_A : \mu_Z \neq \mu_P$ ). The tests will be done at a nominal significance level of  $\alpha = 0.05$ .

The primary efficacy objective will be demonstrated by showing that the t test statistic,  $\frac{|d|}{SE}$ , is greater than  $t_{df,0.975}$  in the modified intent-to-treat population, where  $d$  and  $SE$  are the estimated treatment difference and the estimated standard error of  $d$  from an analysis of covariance (ANCOVA) model with treatment, pooled centers, underlying condition treated with glucocorticoids and baseline LS-BMD Z-score as explanatory variables,  $df$  is the associated degrees of freedom computed from the error term in the model, and  $t_{df,0.975}$  is the

97.5% quantile of the  $t$  distribution with  $df$  degree of freedom. The test and confidence intervals based on this test statistic are robust to the assumptions of normality and of equal variances when within-center treatment group sample size are equal, which is generally the case that treatment allocation is nearly equal within each center because of the manner in which the randomization is carried out. Nevertheless, the underlying assumption of normality and variance homogeneity for the primary analyses will be reviewed and tested by Shapiro's test and Levene's test, respectively, prior to unblinding the data. If the underlying assumption is violated, a transformation or non-parametric approach, such as van Elteren or Cochran-Mantel-Haenszel test (CMH2 from SAS procedure PROC FREQ) adjusted for center, will be applied to the data as appropriate for the hypothesis evaluated.

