#### **9.5.1.2 Change in lumbar spine and total body BMC at Months 6 and 12 relative to baseline**

The change in BMC at the lumbar spine and total body at Month 6 and Month 12 relative to baseline between zoledronic acid and placebo will be evaluated using an ANCOVA model with treatment, pooled centers, underlying condition treated with glucocorticoids and baseline BMC as explanatory variables.

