## 9.8 Sample size calculation

The sample size is calculated to show superiority of zoledronic acid relative to placebo at Month 12.

The null hypothesis of no difference between treatment groups in the mean change in LS-BMD Z-score at Month 12 relative to baseline. In testing this hypothesis, it is assumed that the standard deviations for the two treatment groups is 0.93 under  $H_0$  and  $H_A$ . Based on a primary endpoint of the change in LS-BMD Z-score at 12 months relative to baseline assuming a 0.63 increase in LS-BMD Z-score over 12 months with zoledronic acid and no change in the LS-BMD Z-score in the placebo group and a common standard deviation of 0.93, 82 patients are required to show a significant increase in LS-BMD Z-score at the 0.05 level with 85% power. Adjusting for a dropout rate of 10%, approximately 46 patients per treatment group are required.

The amount of information from controlled trials in a pediatric GIO population is limited. The 0.63 increase in LS-BMD Z-score is based on the increase observed with pamidronate-treated children on chronic glucocorticoid therapy presented in (Acott et al 2005). The common standard deviation of 0.93 was estimated from the pamidronate-treated children and untreated control evaluated in (Acott et al 2005). This standard deviation is consistent with the estimate of the standard deviation obtained from the zoledronic acid group of pediatric osteogenesis imperfecta patients in Study CZOL446H2202. Therefore, it is inferred that the assumption of a 0.63 increase in LS-BMD Z-score over 12 months with ZOL is acceptable.

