Elteren or Cochran-Mantel-Haenszel test adjusted for center, will be applied to the data as appropriate for the hypothesis evaluated.

From the model, the treatment difference between zoledronic acid group vs. placebo group will be estimated and presented together with two-sided 95% confidence interval (CI). P-value will be rounded to the 4th decimal place. In the same table, the Least Squares means and standard errors for change from baseline in lumbar spine Z-score at Month 12 will be presented for each treatment group. Descriptive statistics will also be shown for baseline and Month 12 visits.

A plot will be generated for LS BMD Z-score over time.

Handling of missing values/censoring/discontinuations

In the MITT population, last observation carried forward (LOCF) will be used to impute a value for LS-BMD Z-score at Month 12 for any patient who does not have a Month 12 assessment; however, if a patient prematurely discontinues from the study during the double-blind phase without providing any LS-BMD measurements at Month 6 or Month 12, then a zero percent change in LS-BMD will be assumed at Month 12.

Given that a pediatric population is being studied and patients are expected to experience bone growth during the study, an assumption of zero change over 12 months and LOCF from Month 6 measurements would be considered conservative.

Supportive analyses

Confirmation of the result for the primary efficacy variable will be performed using the per-protocol population without imputation for missing data using the ANCOVA model applied for the primary efficacy analysis.

As another supportive analysis to the primary analysis, the homogeneity of treatment effects across centers will be evaluated by adding the treatment-by-center interaction term into the ANCOVA model employed in the primary efficacy analysis. If $p < 0.1000$ for the treatment-by-center interaction test, which indicates heterogeneous treatment effects across centers, then an additional table will be presented showing the ANCOVA model-based treatment comparisons for primary efficacy variable by each center. Furthermore, interactions between treatment and underlying condition, treatment and baseline tanner stage in pubic hair, treatment and baseline tanner stage in breast development within female population, and treatment and baseline tanner stage in genital stage within male population will be evaluated and presented in a similar way.

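### The named non-parametric fallback for the primary test, and most secondary models, leave out the BMD category used to stratify randomisation; a small, conditional power loss and a low-priority improvement

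*Protocol*

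**What the plan says.** **Randomisation.** Protocol section 5.2 allocates in a "1:1 ratio within one of two treatment arms". Section 5.3 names one stratification factor, taken at screening: "The stratification of randomization will occur based on the baseline BMD value category: -2.0 or less vs. -2.0 to -1.0 vs. -1.0 to -0.5". The SAP, under Pooling of centers, says that four regions serve randomisation as well as analysis. Section 5.3 does not mention region.

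**Analyses that account for the category.** The primary ANCOVA (protocol 9.4.2), the responder analysis (9.4.4) and the Month 6 LS-BMD model (9.5.1.1) include continuous baseline LS-BMD Z-score, as do their SAP counterparts.

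**Primary fallback.** If normality or equal variance fails, protocol 9.4.2 allows a transformation or a non-parametric approach and gives as examples the "van Elteren or Cochran-Mantel-Haenszel test (CMH2 from SAS procedure PROC FREQ) adjusted for center". The SAP repeats this: van "Elteren or Cochran-Mantel-Haenszel test adjusted for center, will be applied to the data as appropriate". Neither document names BMD category or baseline Z-score here.

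**Secondary models.** The BMC model has treatment, pooled centers, "underlying condition treated with glucocorticoids and baseline BMC as explanatory variables" (9.5.1.2). The marker, morphometry, cortical-width and pain models (9.5.1.3, 9.5.1.5 to 9.5.1.7; SAP, Analysis for secondary objectives) have the same form, each with its own baseline. None contains the category or baseline Z-score, and no reason is given. New vertebral fractures are compared by Fisher's exact test, which takes no covariates, and I leave that aside.

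**The concern.** Stratified allocation balances the arms on the stratifier, so the treatment difference varies less from trial to trial than under simple randomisation. If the analysis leaves out a prognostic stratifier, its standard error does not reflect that balance. The test then rejects a true null less often than 5% and has less power than the adjusted test.

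The fallback matters most. It would replace the primary test, and its outcome is the change in the same Z-score that defines the strata. The planned ANCOVA adjusts for that Z-score; the named rank tests would drop it just when the ANCOVA is judged unsuitable.

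**Working it through.** **1. The plan's own figure.** Protocol 9.8 gives a difference of 0.63, SD 0.93 and 85% power ("82 patients are required to show a significant increase in LS-BMD Z-score at the 0.05 level with 85% power"). The test is two-sided ("will be tested against the alternative hypothesis that there is difference between treatment groups") at 0.05 (9.4.2).

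- Normal approximation: n per arm = 2(1.960 + 1.036)² × 0.93² / 0.63² = 39.1, so 40 per arm.
- Two-sample t: 40.11, so 41 per arm, **82 in total**, as stated. Power at 41 per arm is 85.8% (t) or 86.6% (normal).
- Dropout: 41 / 0.90 = 45.6, so 46 per arm and 92 randomised, as stated.

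The sample size is not affected by this point.

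**2. Direction and size in a linear model.** Let R² be the share of residual outcome variance that the category explains, with allocation balanced within it. Let θ = 0.63 / (0.93 × √(2/41)) = 3.067.

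- Type I error, category omitted: 2[1 − Φ(1.96/√(1−R²))]
- Power, category omitted: Φ((θ − 1.96)/√(1−R²))
- Power, category included: Φ(θ/√(1−R²) − 1.96)

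The documents give no R², so the range is assumed. If the relation is linear, correlations of -0.3 and -0.5 cap R² at 0.09 and 0.25.

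| R² | Type I, omitted | Power, omitted | Power, included |
|---|---|---|---|
| 0 | 5.0% | 86.6% | 86.6% |
| 0.05 | 4.4% | 87.2% | 88.2% |
| 0.10 | 3.9% | 87.8% | 89.9% |
| 0.20 | 2.8% | 89.2% | 92.9% |

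The loss is relative to the adjusted test. With total SD held at 0.93, power of the unadjusted test does not fall as R² rises.

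**3. The fallback, by simulation.** Center is read as pooled region. Assumptions: 82 children, baseline Z = -0.5 minus a Gamma(2, 0.75) variable, balance within BMD category, regional mix 30/55/8/7%, region not prognostic, 4,000 trials per setting.

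| Correlation | van Elteren by region | van Elteren by BMD category | Gap (points) | Gap less the 1.8 seen at zero |
|---|---|---|---|---|
| 0 | 82.0% | 83.8% | 1.8 | 0 |
| -0.3 | 82.2% | 85.3% | 3.1 | 1.3 |
| -0.4 | 82.5% | 86.8% | 4.3 | 2.5 |
| -0.5 | 83.1% | 88.7% | 5.6 | 3.8 |

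Type I error, by region against by category, was 4.3% against 5.0% at -0.3 and 3.5% against 5.0% at -0.5.

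A second simulation with the same regional mix (2,500 trials; standard error about 0.7 points for power and 0.4 for type I error) gave:

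- at -0.3, power 81% against 85% and type I error 4.3% against 5.2%;
- at -0.5, power 84% against 90% and type I error 3.3% against 4.3%.

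The gap at zero correlation, where the category carries no information, comes from splitting on small regions.

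**4. Secondary models, by simulation.** Each model had its own baseline, 82 children and an assumed standardised effect of 0.677 (0.63/0.93); the documents plan no effect for these endpoints. At a partial R² of 0.07 to 0.11 for the category, omitting it gave type I error of 3.9-4.1% and cost about 1.5 to 3.5 points of power. At a partial R² of zero there was no material change.

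**The case against.** **The tests are examples.** The fallback applies only if the assumption checks fail. The wording also allows a transformation, which could keep the ANCOVA with baseline Z-score. This stands: a reader might infer that the plan commits the primary conclusion to a center-only rank test, and it does not.

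**Region may itself be a randomisation factor.** The SAP says so, and the robustness argument in protocol 9.4.2 relies on near-equal allocation within centers. A reader might infer that these analyses ignore the randomised grouping altogether. On the SAP's wording they keep one part of it, and a fallback stratified by BMD category alone would drop that part. In a check with allocation balanced on both factors and correlation -0.3, the category-only test was about as conservative as the region-only one (type I error 4.3% against 4.4%). When region was assumed to explain 10% of the variance, region-only power was 85.7% against 85.1% at -0.3, and 82.5% against 80.9% at zero (1,500 trials, error about 1 point). This stands, and it shapes the fix.

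**The power gap is only partly due to the omission.** This stands. At -0.3 an unstratified Wilcoxon test had 84.5% power, against 85.1% by BMD category and 82.1% by region. The region test is below the planned 85% even at zero correlation, so the omission does not cause that shortfall.

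**The secondary models already carry their own baselines.** This stands as a limit on size. Protocol 9.5.1 also makes no multiplicity-controlled claim on these endpoints. For pain, extra terms in a logistic model with about 82 children risk sparse cells and change the conditional odds ratio.

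None of this gives a reason for leaving the category and baseline Z-score out.

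**Conclusion.** The point holds in a limited form. The named fallback tests, and five groups of secondary models, omit both the stratifier in protocol 5.3 and the covariate that stands in for it elsewhere. They are conservative and lose power only to the extent that the category is prognostic beyond what each model already contains.

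For the fallback, at assumed correlations of -0.3 to -0.5, that means about 81-84% power by region against 85-90% by BMD category, with type I error of about 3.3-4.3%. About 2 points of the power gap are not due to the omission. These figures rest on an assumed correlation, baseline distribution and regional mix, and on region being neither prognostic nor a randomisation factor. For the secondary endpoints the loss is smaller and may be nil.

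Two stronger readings are not supported. One is that the primary analysis ignores the stratification: the planned ANCOVA includes baseline Z-score and is unaffected. The other is that false-positive risk rises: the error goes in the conservative direction. Low priority; a free improvement.

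**What to change.** 1. **Reconcile the randomisation factors.** Protocol 5.3 names BMD category only; the SAP's Pooling of centers adds region. State which applied. State also whether center in the fallback means pooled region: with about 30 centers for 92 children (protocol section 4), individual centers would average about three patients.
2. **Name a fallback that keeps those factors.** Preferably a rank ANCOVA with baseline LS-BMD Z-score and pooled region, with the algorithm written out. If region was not a randomisation factor, a van Elteren test stratified by BMD category would serve. If both factors were used, crossing them gives 3 × 4 = 12 cells, about seven children each (82/12), which favours the rank ANCOVA.
3. **Continuous secondary ANCOVA models.** Add baseline LS-BMD Z-score (one degree of freedom) or the BMD category (two), or justify leaving them out.
4. **Pain logistic model.** Add the single Z-score term only if the cells are not too sparse.

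The cost is SAP wording, settled before unblinding, and one or two degrees of freedom per model. Both variables are already collected. The sample size and the planned primary ANCOVA do not change.
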